10.7 Adjustment for Site

The study may be performed at more than one site. If so the effect of site will be investigated in each of the analyses above.

For the principal endpoint analysis, a fixed effects model with site as the effect will determine if the percentage change from baseline or log of the ratio of post-treatment result to baseline result as the outcome will need to be adjusted for that effect. A p-value of ≤ 0.05 will constitute statistical significance of the site effect.

The same analysis will be done for the mean change in SUI episodes per day secondary endpoint analysis. Site will be a fixed effect modeling each subject's change in mean number of SUI episodes per day.

For the quality of life repeated measures ANOVA site will again be included in the model as a fixed effect.

Should site become statistically significant in any of the analyses then it will be used as a fixed effect factor in all three analyses, and the appropriate percentage and mean changes (or log transformations implementing those analyses) will be extracted from the output created by the models.

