- b. For the quality of life score there will be three measures as described in the visit schedule above. For descriptive purposes the results and change from the previous visit will be shown, as well as the change from the enrollment visit to the post-treatment visit. The changes will likely be negative scores as the QOL is expected to improve, as the instrument records lower numbers as indicating a better quality of life. For the purposes of inferential analysis, a mixed model analysis of variance on the scores will be used on the result at time t (t=baseline, post-control, post-treatment) with time as a fixed effect and subject as a random effect. Thus, the null hypothesis is that there is no significant difference from baseline/enrollment to post-treatment, i.e., that the mean change in score is 0. The alternative is that this change is less than 0. Correlation of scores within subjects will be considered as compound symmetric. The p-value indicating the significance of the least square mean score at the third time-point compared to that at the first time-point will determine if the endpoint is met.

All inferential testing will be done on the mITT population and will be one-sided. As noted above statistical significance will be reached if the relevant p-value is less than 0.0167. Results for all populations will be reported.

There is a secondary safety endpoint as described earlier in the protocol. Safety reporting using urinalysis, vaginal swab, vaginal examination, and evaluation will be descriptive and narrative in nature.

Similarly, exploratory endpoint results of comfort and successful use will be descriptive. No inferential hypotheses will be used here.

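### The QoL site check tests sites' average QoL level, not their QoL change, so baseline severity alone can switch the primary and SUI-episode models to site adjustment

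*Combined protocol and SAP*

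**What the plan says.** Section 10.4, item 3b sets out the QoL analysis: "a mixed model analysis of variance on the scores will be used on the result at time t", where the times are baseline, post-control and post-treatment, "with time as a fixed effect and subject as a random effect". On the covariance it adds: "Correlation of scores within subjects will be considered as compound symmetric". Success rests on a change: "The p-value indicating the significance of the least square mean score at the third time-point compared to that at the first time-point" decides whether the endpoint is met.

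Section 10.7 then checks site for each of the three inferential endpoints, at p ≤ 0.05.

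- Primary: the outcome in the site model is each woman's percentage change or log ratio.
- SUI episodes: "Site will be a fixed effect modeling each subject's change in mean number of SUI episodes per day".
- Quality of life: "For the quality of life repeated measures ANOVA site will again be included in the model as a fixed effect".

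The consequence is shared: "Should site become statistically significant in any of the analyses then it will be used as a fixed effect factor in all three analyses".

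Section 10.6 plans no covariates, so nothing else takes baseline severity out of the QoL site test. The Protocol Summary gives four enrolling sites.

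**The concern.** The first two checks ask whether change under the device differs between sites. The QoL check, as worded, asks whether women at different sites have different QoL scores averaged over three visits. Two of those visits precede device use, so the answer is mostly about who each site recruits. Section 5.3 draws women from the investigators' own patients and from the public, so case-mix differences between sites are plausible.

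Two things follow. A site whose women are more bothered at enrollment can make the QoL site term significant when the device does the same everywhere, and the shared rule then alters the primary and SUI-episode models for a reason unconnected with the device. Conversely, a real site difference in QoL change is diluted, because it enters only one of the three visits being averaged.

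**Working it through.** **The plan's own figures.** The documents state no operating characteristic for any site test. The only power figures are in Table 1 of 10.3. They reproduce as the probability that a one-sided 95% t half-width is no larger than the stated value at n = 50: 0.999, 0.991, 0.957, 0.872, 0.726 and 0.995, against 0.999, 0.991, 0.956, 0.869, 0.720 and 0.995. This confirms the basis n = 50 but says nothing about site.

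**Inputs.** From the documents: 4 sites, n = 50, three visits, compound symmetry, site threshold 0.05. Assumed: sites of 13/13/12/12, single-visit SD of 1, within-woman correlation ρ of 0.5, 0.7 or 0.8, complete data. The deviating site has 13 women.

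**What the site term tests.** With complete data and compound symmetry, the site term in a time + site model is a one-way F test on each woman's three-visit mean, with 3 and 46 df (critical value 2.81).

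- Variance of a three-visit mean: (1 + 2ρ)/3 = 0.667, 0.800, 0.867.
- Variance of a change (visit 3 minus visit 1): 2(1 − ρ) = 1.0, 0.6, 0.4.
- Noncentrality when one site of 13 is shifted by δ: λ = (13 × 37/50) δ²/variance = 9.62 δ²/variance.

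**Scenario (a): level differs, change identical.** The whole of δ enters the three-visit mean and none enters the change.

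**Scenario (b): same level at both pre-device visits, three sites improve by 0.8 SD and one does not.** The change shifts by 0.8, but the three-visit mean shifts by only 0.8/3 = 0.267.

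| Scenario and test | λ at ρ = 0.5 / 0.7 / 0.8 | Probability of p ≤ 0.05 |
|---|---|---|
| (a) δ = 0.5, planned test | 3.61 / 3.01 / 2.77 | 30% / 25% / 24% |
| (a) δ = 0.75, planned test | 8.12 / 6.76 / 6.24 | 62% / 53% / 50% |
| (a) either δ, test on change | 0 | 5% |
| (b) planned test | 1.03 / 0.86 / 0.79 | 11% / 10% / 10% |
| (b) test on change | 6.16 / 10.26 / 15.39 | 49% / 73% / 90% |

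Simulation of 20,000 trials per scenario agrees to about one point. In (b), a full site-by-time test (6 and 92 df) detects the difference in 51%, 77% and 93%.

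**Chance that the shared switch fires.** If the three site tests are treated as independent, with no site effect anywhere, it is 1 − 0.95³ = 14%. With a QoL level difference at ρ = 0.7, it is 1 − 0.95² × (1 − 0.53) = 58% for 0.75 SD and 1 − 0.95² × (1 − 0.255) = 33% for 0.5 SD. The tests use the same women, so independence is only a convenience.

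**Effect on the QoL result.** Site is constant within a woman, so with complete data it cannot move a within-woman contrast. Models fitted to simulated data with sites of 20/15/10/5 gave −0.49197 (SE 0.11409) for visit 3 versus visit 1, with and without site. With five post-treatment scores missing, the estimates were −0.3357 and −0.3366.

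**Effect on the primary.** Assume that the overall mean taken from the site model weights sites equally and that the residual SD is unchanged. The SE is then multiplied by √50 × √(Σ 1/nⱼ)/4. Take a true mean reduction of 60% against 50% and SD 20 (both from 10.3), tested one-sided at 0.0167. Without site, the noncentrality is 10/(20/√50) = 3.54 and power is 90.8%.

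- 13/13/12/12: SE × 1.0008, power 90.6%.
- 20/15/10/5: Σ 1/nⱼ = 0.4167, SE × 1.141, noncentrality 3.10, power 81.4%.

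**The case against.** The strongest reply is that little harm to a result has been shown. The QoL contrast does not move with complete data, and with balanced sites a false trigger costs the primary about 0.1 point of power. Both stand. The larger loss with uneven sites comes from how an adjusted model weights sites, and any trigger would incur it. The present point governs only how often that happens for an irrelevant reason. The trigger rates also rest on assumed level differences, correlations and site sizes.

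A reader might go on to three stronger conclusions that the documents do not support.

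- That site differences in device effect would almost never be seen in this trial. The primary and SUI-episode checks model change and test such differences directly. Even for QoL, the power in the scenario above is low (10% to 11%) rather than nil.
- That the QoL result would be presented, for labeling, as free of a site effect. Section 10.7 decides whether to adjust; it promises no statement on consistency across sites.
- That the QoL estimate is itself distorted by adding site. It is not, as the fits show.

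It can also be said that 10.2 promises a more detailed SAP, which could name the interaction. It could, but 10.7 already fixes the QoL term, the threshold and the carry-over, and nothing supplied departs from them.

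**Conclusion.** The point holds, limited to the QoL check. As written, that check tests level and not change, which is inconsistent with both the endpoint and the other two checks. Following the stated rule lets baseline severity alone put site into the primary and SUI-episode models: about 24% to 62% of trials for one site 0.5 to 0.75 SD worse, where a test on change would give 5%. It also detects a site with no QoL benefit in about 10% to 11% of trials, where a test on change would do so in 49% to 90%. These figures assume 13/13/12/12 sites, correlation 0.5 to 0.8, compound symmetry and complete data.

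The consequence for the primary depends on site balance: negligible when sites are equal, and a fall from 90.8% to 81.4% power at SD 20 with sites of 20/15/10/5 and equally weighted site means. It should be corrected because the rule is wrong as stated and the remedy is cheap, not because a trial conclusion has been shown to fail.

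**What to change.** In 10.7, replace the QoL sentence with wording such as: *For quality of life, site will be tested as a fixed effect on each subject's change in score from enrollment to post-treatment.* Testing the site-by-time contrast for the third versus the first time point in the mixed model addresses the same question.

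Add that a site difference in QoL level does not trigger adjustment of any endpoint. If site is kept in the QoL model, include site-by-time, so that the adjustment acts on the contrast being tested. Carry the same wording into the SAP.

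The cost is a short edit to 10.7, one model term in the SAS code and no new data or participants. The statistical price is a few degrees of freedom: with four sites and three visits, 3 for the single contrast or 6 for the full interaction.

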10.8 Adverse Events

No formal testing of adverse events or their characteristics will be performed. Reporting is described above. The latest version of MedDRA will be used for coding. The section of tables will include a summary table, a system organ class/preferred term table, and tables for relationship and severity to study treatments.

10.9 Interim Analyses and Stopping Criteria.

No interim analyses are planned, and the study will be run to its completion unless stopped for safety considerations.

11 SOURCE DOCUMENTS AND ACCESS TO SOURCE DATA/DOCUMENTS

Each participating site will maintain appropriate medical and research records for this trial, in compliance with ICH E6 and regulatory and institutional requirements for the protection of confidentiality of participants. As part of participating in a NIH IC-sponsored or NIH IC -affiliated study, each site will permit authorized representatives of the NIH IC and regulatory agencies to examine (and when permitted by applicable law, to copy) clinical records for the purposes of quality assurance reviews, audits, and evaluation of the study safety, progress, and data validity. Describe in this section who will have access to records.

12 QUALITY ASSURANCE AND QUALITY CONTROL

Following written SOPs, the monitors will verify that the clinical trial is conducted and data are generated, documented (recorded), and reported in compliance with the protocol, GCP, and the applicable regulatory requirements (e.g., Good Laboratory Practices (GLP), Good Manufacturing Practices (GMP)).

The investigational site will provide direct access to all trial related sites, source data/documents, and reports for the purpose of monitoring and auditing by the sponsor, and inspection by local and regulatory authorities.

13 ETHICS/PROTECTION OF HUMAN SUBJECTS

13.1 ETHICAL STANDARD

The investigator will ensure that this study is conducted in full conformity with Regulations for the Protection of Human Participants of Research codified in 45 CFR Part 46, 21 CFR Part 50, 21 CFR Part 56, and/or the ICH E6.

13.2 INSTITUTIONAL REVIEW BOARD

The protocol, informed consent form(s), recruitment materials, and all participant materials will be submitted to the IRB for review and approval. Approval of both the protocol and the consent form must be obtained before any participant is enrolled. Any amendment to the protocol will require review and approval by the IRB before the changes are implemented to the study. All changes to the consent form will be IRB approved; a determination will be made regarding whether previously consented participants need to be re-consented.

13.3 INFORMED CONSENT PROCESS

13.3.1 CONSENT/ASSENT AND OTHER INFORMATIONAL DOCUMENTS PROVIDED TO PARTICIPANTS Consent forms describing in detail the study agent, study procedures, and risks are given to the participant, and written documentation of informed consent is required prior to starting intervention/administering study product. The following consent materials are submitted with this protocol Rinovum Subsidiary 2, LLC. SUI Device Efficacy and Safety Study Informed Consent.

Informed consent is a process that is initiated prior to the individual's agreeing to participate in the study and continues throughout the individual's study participation. Extensive discussion of risks and possible benefits of participation will be provided to the participants and their families. Consent forms will be IRB-approved and the participant will be asked to read and review the document. The investigator will explain the research study to the participant and answer any questions that may arise. All participants will receive a verbal explanation in terms suited to their comprehension of the purposes, procedures, and potential risks of the study and of their rights as research participants. Participants will have

the opportunity to carefully review the written consent form and ask questions prior to signing.

The participants will have the opportunity to discuss the study with their surrogates or think about it prior to agreeing to participate. The participant will sign the informed consent document prior to any procedures being done specifically for the study. The participants may withdraw consent at any time throughout the course of the trial. A copy of the informed consent document will be given to the participants for their records. The rights and welfare of the participants will be protected by emphasizing to them that the quality of their medical care will not be adversely affected if they decline to participate in this study.

13.4 PARTICIPANT AND DATA CONFIDENTIALITY

Participant confidentiality is strictly held in trust by the participating investigators, their staff, and the sponsor(s) and their agents. This confidentiality is extended to cover testing of biological samples and genetic tests in addition to the clinical information relating to participants. Therefore, the study protocol, documentation, data, and all other information generated will be held in strict confidence. No information concerning the study or the data will be released to any unauthorized third party without prior written approval of the sponsor.

The study monitor, other authorized representatives of the sponsor, representatives of the IRB or pharmaceutical company supplying study product may inspect all documents and records required to be maintained by the investigator, including but not limited to, medical records (office, clinic, or hospital) and pharmacy records for the participants in this study. The clinical study site will permit access to such records.

The study participant's contact information will be securely stored at each clinical site for internal use during the study. At the end of the study, all records will continue to be kept in a secure location for as long a period as dictated by local IRB and Institutional regulations.

Study participant research data, which is for purposes of statistical analysis and scientific reporting, will be transmitted to and stored at the East Suburban OB/GYN Facility. This will not include the participant's contact or identifying information. Rather, individual participants and their research data will be identified by a unique study identification number. The study data entry and study management systems used by clinical sites and by the [insert institution] research staff will be secured and password protected. At the end of the study, all study databases will be de-identified and archived at the [insert institution].

13.5 FUTURE USE OF STORED SPECIMENS

Data collected for this study will be analyzed and stored at the [insert institution] facility. After the study is completed, the de-identified, archived data will be transmitted to and stored at the Sponsor's facility under the supervision of the Director of Regulatory and Quality for use by other researchers including those outside of the study. Permission to transmit data to the will be included in the informed consent.

14 DATA HANDLING AND RECORD KEEPING

14.1 DATA COLLECTION AND MANAGEMENT RESPONSIBILITIES

Data collection is the responsibility of the clinical trial staff at the site under the supervision of the site PI. The investigator is responsible for ensuring the accuracy, completeness, legibility, and timeliness of the data reported.

All source documents should be completed in a neat, legible manner to ensure accurate interpretation of data. Black ink is required to ensure clarity of reproduced copies. When making changes or corrections, cross out the original entry with a single line, and initial and date the change. **DO NOT ERASE, OVERWRITE, OR USE CORRECTION FLUID OR TAPE ON THE ORIGINAL.**

Copies of the CRF will be provided for use as source documents and maintained for recording data for each participant enrolled in the study. Data reported in the CRF derived from source documents should be consistent with the source documents or the discrepancies should be explained and captured in a progress note and maintained in the participant's official electronic study record.

Clinical data (including AEs, concomitant medications, and expected adverse reactions data) and clinical laboratory data will be entered into Case Report Forms manually.

14.2 STUDY RECORDS RETENTION

Study documents should be retained for a minimum of 2 years after the last approval of a marketing application in an ICH region and until there are no pending or contemplated marketing applications in an ICH region or until at least 2 years have elapsed since the formal discontinuation of clinical development of the investigational product. These documents should be retained for a longer period, however, if required by local regulations. No records will be destroyed without the written consent of the sponsor, if applicable. It is the responsibility of the sponsor to inform the investigator when these documents no longer need to be retained.

14.3 PROTOCOL DEVIATIONS

A protocol deviation is any noncompliance with the clinical trial protocol, GCP, or MOP requirements. The noncompliance may be either on the part of the participant, the investigator, or the study site staff. As a result of deviations, corrective actions are to be developed by the site and implemented promptly.

These practices are consistent with ICH E6:

- 4.5 Compliance with Protocol, sections 4.5.1, 4.5.2, and 4.5.3
- 5.1 Quality Assurance and Quality Control, section 5.1.1
- 5.20 Noncompliance, sections 5.20.1, and 5.20.2.

It is the responsibility of the site to use continuous vigilance to identify and report deviations within 3 working days of the scheduled protocol-required activity. All deviations must be addressed in study source documents, reported to the Sponsor. Protocol deviations must be sent to the local IRB per their guidelines. The site PI/study staff is responsible for knowing and adhering to their IRB requirements. Further details about the handling of protocol deviations will be included in the MOP.]

14.4 PUBLICATION AND DATA SHARING POLICY

This study will comply with the NIH Public Access Policy, which ensures that the public has access to the published results of NIH funded research. It requires scientists to submit final peer-reviewed journal manuscripts that arise from NIH funds to the digital archive [PubMed Central](#) upon acceptance for publication.

The International Committee of Medical Journal Editors (ICMJE) member journals have adopted a clinical trials registration policy as a condition for publication. The ICMJE defines a clinical trial as any research project that prospectively assigns human participants to intervention or concurrent comparison or control groups to study the cause-and-effect

relationship between a medical intervention and a health outcome. Medical interventions include drugs, surgical procedures, devices, behavioral treatments, process-of-care changes, and the like. Health outcomes include any biomedical or health-related measures obtained in patients or participants, including pharmacokinetic measures and adverse events. The ICMJE policy, and the Section 801 of the Food and Drug Administration Amendments Act of 2007, requires that all clinical trials be registered in a public trials registry such as ClinicalTrials.gov, which is sponsored by the National Library of Medicine. Other biomedical journals are considering adopting similar policies. For interventional clinical trials performed under NIH IC grants and cooperative agreements, it is the grantee's responsibility to register the trial in an acceptable registry, so the research results may be considered for publication in ICMJE member journals. The ICMJE does not review specific studies to determine whether registration is necessary; instead, the committee recommends that researchers who have questions about the need to register err on the side of registration or consult the editorial office of the journal in which they wish to publish.

FDAAA mandates that a "responsible party" (i.e., the sponsor or designated principal investigator) register and report results of certain "applicable clinical trials":

- Trials of Drugs and Biologics: Controlled, clinical investigations, other than Phase I investigations, of a product subject to FDA regulation;
- Trials of Devices: Controlled trials with health outcomes of a product subject to FDA regulation (other than small feasibility studies) and pediatric post-market surveillance studies.

NIH grantees must take specific steps to ensure compliance with NIH implementation of FDAAA.]

